### **Study Drug Accountability Exposure**

Study drug accountability exposure is tabulated as a continuous variable for the safety analysis set, and includes the following parameters:

- Time from first kit dispensed to last kit returned (weeks), derived as (latest kit return date – earliest kit dispense date + 1)/7. Subjects who were dispensed at least 1 kit but never returned any kit are credited with 1 day.
- Cumulative zavegepant exposure (sprays) based on kits dispensed and returned, derived as summing (4 - number of unused devices remaining in each kit) across records with non-missing kit dispense and return dates.
- Average zavegepant exposure (sprays per month) based on kits dispensed and returned, derived as  $4 \times$  cumulative zavegepant exposure based on kits dispensed and returned/time from first kit dispensed to last kit returned.

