7.4 Study and Treatment Compliance

Responsible study personnel will dispense the study drug to the study subjects. Subjects should use all devices in one box/container before starting to use the devices in the next container. Accountability and compliance verification should be documented in the subject's study records.

Subjects must be counseled at all study visits on the importance of taking the study drug as directed. Treatment compliance, through review of study drug doses reported electronically, and review of the returned study drug, should be assessed by site staff at each study visit. Discrepancies between doses reported electronically, review of study drug, and information provided by subject, must be documented in the source record. Incorrect or missing dosing data and migraine data that are reported in the eDiary will be corrected through either a Data Clarification Record or a Medication Reconciliation Form, as appropriate.

Investigators should inform subjects that involuntary termination from the study will occur in cases where non-compliance is identified (defined as both non-compliance with the daily evening report and/or with average number of monthly doses of study drug). Study staff should contact a subject in between the monthly study visits if the subject demonstrates non-compliance the daily evening migraine report and document the contact in the source notes, to identify potential lost to follow up or non-compliant subjects as early as possible.

Investigators must monitor subjects for possible cases of abuse of study drug (patients taking study drug for non-therapeutic purposes, e.g. for psychoactive effects such as high or euphoria). Investigators should assess study drug accountability discrepancies (e.g. missing study drug, loss of drug, or non-compliance cases in which more study drug was used, as compared to expected). Investigators should obtain more information and explanation from patients when there are study drug accountability discrepancies. See Section 8.1.1.

Cases of potential study drug abuse or overdose (including cases of non-compliance with study drug dosing instructions or patients who discontinue treatment without returning study drug) should be documented in the source record and reported as an AE or SAE as appropriate. Dosing

errors (e.g. accidentally administering 2 sprays from 2 devices in one calendar day) should be reported as deviations.

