### **6.2.6      *Exposure***

Study drug is zavegepant 10 mg IN spray.

Subjects provide study drug taken status (yes, no), number of sprays administered, and nostril location of each spray (left, right) in the eDiary every day after they are determined to be eligible to take study drug. Sites may enter this information on the eDiary medication reconciliation form for missed doses. Days on which a subject took study drug are determined by records with non-missing study drug date/time (see Section 7.1). If there are no study drug data in the eDiary on a given day, then it is assumed that the subject did not take study drug that day.

Study drug accountability is provided by the site on the Drug Accountability CRF. There are 4 single-use devices in each kit. Sites provide the number of unused devices in each kit dispensed and returned.

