### **eDiary Versus Drug Accountability Cumulative Study Drug Exposure**

eDiary versus drug accountability cumulative study drug exposure is tabulated as the number and percentage of subjects in the safety analysis set with 0,  $\geq 10$ ,  $\geq 20$ ,  $\geq 30$ ,  $\geq 40$ ,  $\geq 50$  absolute spray difference, derived as the absolute value of (eDiary study drug cumulative exposure [sprays] – study drug accountability cumulative exposure [sprays]).

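### Kit-accountability exposure counts no sprays from unreturned kits, and the unsigned eDiary comparison pools non-return with unreported use

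*SAP*

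**What the plan says.** In SAP 6.2.6.1, the part on study drug accountability exposure defines three parameters for the safety analysis set.

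- **Time**, in weeks, is "derived as (latest kit return date – earliest kit dispense date + 1)/7", with one exception: "Subjects who were dispensed at least 1 kit but never returned any kit are credited with 1 day".
- **Cumulative sprays** are "derived as summing (4 - number of unused devices remaining in each kit) across records with non-missing kit dispense and return dates".
- **Average sprays per month** is 4 times "cumulative zavegepant exposure based on kits dispensed and returned/time from first kit dispensed to last kit returned".

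SAP 6.2.6 fixes the kit size: "There are 4 single-use devices in each kit".

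The next table compares the two sources, again for the safety set. The difference is "derived as the absolute value of" the eDiary total minus the accountability total. It is shown as 0, ≥ 10, ≥ 20, ≥ 30, ≥ 40 and ≥ 50 sprays.

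Three other provisions bear on the point. Safety-set membership (SAP 4.1) needs a study drug start date, which SAP 7.1 takes from an eDiary or medication reconciliation record with more than zero sprays. SAP 6.2.6 treats a day without eDiary drug data as a day without drug. SAP 6.1.3 rules out imputation, but nothing says whether a sum over no returned kits is 0 or missing.

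**The concern.** Use from a kit that does not come back is unknown: anything from 0 to 4 sprays. The derivation treats it as none. For a subject who returned nothing, the credited day puts an invented duration into the time row. If the empty sum is read as 0, it also puts zero sprays next to a subject who, by definition of the safety set, has at least one recorded spray.

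Non-return is not a neutral kind of missingness here. Protocol 7.4 asks investigators to assess accountability discrepancies such as "missing study drug, loss of drug, or non-compliance cases in which more study drug was used, as compared to expected", and it names stopping treatment without returning drug among the cases of potential abuse or overdose. The accountability tables thus understate use in subjects whom the protocol wants examined. Taking the absolute difference then removes the sign, which is what separates eDiary above accountability (non-return) from accountability above eDiary (unreported use). At stake is how useful these two summaries are as a cross-check on reported dosing.

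**Working it through.** The plan states no figure on this point, so there is nothing to reproduce. The check applies the SAP's formulas to constructed subjects.

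**Inputs and formulas (SAP 6.2.6 and 6.2.6.1).** Each kit holds 4 devices.

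- Sprays = sum of (4 − unused) over returned kits.
- Time = (last return − first dispense + 1)/7 weeks, or 1/7 week if nothing was returned.
- Average = 4 × sprays/time.
- Signed difference = eDiary − accountability. The table shows only its absolute value.

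**Assumed schedule.** One kit is dispensed every 28 days from day 1. A kit that is returned comes back 28 days later.

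| Constructed subject | eDiary | Accountability sprays | Time (weeks) | Average per month | Signed difference | Row |
|---|---|---|---|---|---|---|
| A. 3 kits, none returned | 12 | 0 (empty sum read as 0) | 1/7 = 0.143 | 4 × 0/0.143 = 0 | +12 | ≥ 10 |
| B. 6 kits, all returned empty, 12 sprays unreported | 12 | 6 × 4 = 24 | 169/7 = 24.143 | 4 × 24/24.143 = 3.98 | −12 | ≥ 10 |
| C. 13 kits, all used, 3 mid-study kits unreturned | 52 | 10 × 4 = 40 | 365/7 = 52.143 | 4 × 40/52.143 = 3.07 | +12 | ≥ 10 |
| D. As C, but the last 3 kits unreturned | 52 | 40 | 281/7 = 40.143 | 4 × 40/40.143 = 3.99 | +12 | ≥ 10 |
| E. 3 unreturned kits (12 reported sprays), then 3 returned kits (12 unreported) | 12 | 3 × 4 = 12 | 169/7 = 24.143 | 4 × 12/24.143 = 1.99 | 0 | 0 |

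**What the rows show.**

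1. With every kit returned, C would average 4 × 52/52.143 = 3.99. The missing mid-study kits remove 12/52 = 23% of both the sprays and the average.
2. In D the same 12 sprays are lost, but time shortens too, so the average is preserved. The average is biased only when unreturned kits lie inside the dispense-to-last-return span. Cumulative sprays are short in both cases.
3. A and B are opposite errors in the same row.
4. E has 12 sprays of each error and is counted as full agreement.

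**Trial level, illustrative only.** If a share q of subjects is scored 0 and the others average m, the tabulated mean is (1 − q) × m. With m = 40 and q from 1% to 10% of 600 (6 to 60 subjects), it runs from 39.6 to 36.0. Both q and m are assumptions. Equating the shortfall with bias also assumes that non-returners used as much as the others.

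**The case against.** The strongest reply is that the plan already separates these cases outside the two tables. One listing in SAP 6.2.6.1 shows dispensed and returned status, dates and unused devices for every kit. Another shows both cumulative totals per subject and flags absolute differences of 10 or more. SAP 6.2.6.2 counts discontinued subjects who failed to return at least one kit, or any kit. A reader might infer that the plan as a whole cannot tell non-return from unreported use. It can, subject by subject; the fault is confined to the summaries. The 6.2.6.2 count uses the full analysis set and is not crossed with the spray difference, so it repairs neither table.

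A reader might also take accountability to be the only check on self-reported dosing. It is not. Protocol 7.4 has sites compare reported doses with returned drug at each visit and correct wrong or missing dosing data. Under SAP 6.2.6 and 7.1, reconciliation-form records enter the eDiary exposure. Large unreported use would have to survive that process.

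Nor does the link to abuse extend to exploratory objective 1. That endpoint counts AEs, and SAP 3.2 takes AEs from the AE CRFs, not from spray differences.

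Two further replies have force. The parameter names say that they rest on kits dispensed and returned, so they do not claim to measure total use. And because drug is due back at every treatment visit, a subject who returns nothing probably left early with few sprays, so the illustrative falls in the mean are likely to overstate the bias.

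What remains is that two planned tables give understated or ambiguous values under their stated rules.

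**Conclusion.** The point holds for the accountability summary and for the eDiary-versus-accountability table. Accountability sprays fall short by the number of devices used from unreturned kits, 0 to 4 per kit. The monthly average falls short when those kits lie within the measured span. The comparison table cannot show the direction of a discrepancy and can show agreement where two errors offset.

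That a never-returner scores 0 sprays over 1/7 week is the arithmetic reading. The credited day suggests that such subjects are retained, but the SAP does not say so. If the empty sum is programmed as missing, they drop out of the spray rows and the comparison instead, and the illustrative falls in the mean disappear. Partial returners are undercounted under either reading.

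The documents give no non-return rate, so the trial-level effect is unknown. It should not be read as reaching the safety conclusions: the primary endpoints, patient-years, exposure subgroups and exposure-adjusted rates do not use accountability data. The change is worth making because it is cheap and these tables are meant as a cross-check on dosing.

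**What to change.** 1. Delete the 1-day credit. For subjects who returned no kit, set accountability time, sprays and average to missing, and report how many such subjects there are.
2. Show accountability exposure separately for subjects who returned every dispensed kit and for those with any unreturned kit. For the second group, give the number of unreturned kits and bounds of 0 to 4 sprays per kit. Keep both groups in view, since the all-returned group alone selects the most compliant subjects.
3. Tabulate the eDiary-versus-accountability difference with its sign, split by the same return status, and count never-returners as not evaluable.

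The sign alone is not enough: subject E would still show 0. With the split, E sits in the unreturned group with accountability bounds of 12 + 0 = 12 to 12 + 12 = 24 sprays, hence a difference between 0 and −12.

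SAP Section 8 does not exempt these tables from the interim CSR. There, kits still held by ongoing subjects should be kept apart from kits not returned by discontinued subjects, a distinction that 6.2.6.2 already draws.

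The cost is SAP wording and reprogramming from the existing Drug Accountability CRF and eDiary data, with a smaller N in the all-returned row. No new data collection is needed.

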### **eDiary Versus Drug Accountability Cumulative Study Drug Exposure**

eDiary versus drug accountability cumulative study drug exposure is tabulated as the number and percentage of subjects in the safety analysis set with 0,  $\geq 10$ ,  $\geq 20$ ,  $\geq 30$ ,  $\geq 40$ ,  $\geq 50$  absolute spray difference, derived as the absolute value of (eDiary study drug cumulative exposure [sprays] – study drug accountability cumulative exposure [sprays]).

### 6.2.6.2 *Measurements of Treatment Compliance*

#### eDiary Usage Compliance

eDiary usage compliance is tabulated for the safety analysis set, for each source (subject; subject or site). Data days are records with complete eDiary finding dates. Usage compliance is derived for the following parameters:

- Last 28 days before LTT start:  $100 \times (\text{total number of data days from the [LTT start date} - 28 \text{ days}] \text{ to the [LTT start date} - 1 \text{ day}]) / 28$
- LTT start to LTT end:  $100 \times (\text{total number of data days from the LTT start date to the LTT end date}) / (\text{LTT end date} - \text{LTT start date} + 1)$ .

eDiary usage compliance is tabulated as a continuous variable and as the number and percentage of subjects in the following categories:  $\geq 90\%$  compliance;  $\geq 80\%$  compliance. Subject sources are the evening report, PoM, and SM. The site source is the medication reconciliation form.

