	The screening phase includes a screening visit and a 28-day Observation Phase. Upon completion of the screening visit, subjects will electronically

[figure not shown]
record migraine occurrence every day. If a migraine occurs, subjects record migraine intensity and whether the migraine was treated. Subjects will report all concomitant medications, including migraine standard of care medications, in a concomitant medication log.

During the 28-day observation phase, the subject will return to the clinic for the pre-baseline visit. At the pre-baseline visit, a blood sample for laboratory tests will be collected.

After the pre-baseline visit, subjects will return to the clinic for the baseline visit. At the baseline visit, eligibility for continued participation in the study will be assessed. After the investigator reviews the results of the pre-baseline laboratory assessments and all other eligibility criteria, eligible subjects may be dispensed study drug and may start dosing in the long-term treatment phase. If eligible for the long-term treatment phase, subjects will be instructed that they can take study drug at the onset of a migraine. Subjects will be instructed that they can treat a maximum of 8 migraines per month (28 days) during the long-term treatment phase and that only one administration of study drug is allowed per calendar day. Subjects are required to continue to electronically record their migraine occurrence and migraine intensity daily. If the subject administers study drug to treat a migraine, the dose of study drug must also be reported on that day. Subjects will continue to record any concomitant medication use (including migraine standard of care medications) in the paper diary throughout the course of the study.

Subjects will have study visits at Week 2, Week 4 and every 4 weeks through Week 52. The Week 52 (+/- 7 days) visit is the end of treatment visit. There is a follow up visit 14 days (+/- 2 days) after the Week 52/end of treatment visit (see Table 1).

STUDY SCHEMATIC

Total study duration approximately 58 weeks

TABLE OF CONTENTS

1 IN	TRODUCTION AND RATIONALE	.14
1.1	THERAPEUTIC AREA BACKGROUND	.14
1.2	PRODUCT DEVELOPMENT BACKGROUND	.15
1.2.1	NON-CLINICAL PHARMACOLOGY	.15
1.2.1.1	NONCLINICAL PHARMACOKINETICS, PHARMACODYNAMICS,	
	AND TOXICOLOGY	.15
1.2.2	CLINICAL EXPERIENCE	.15
1.2.2.1		
1.2.2.2		
1.2.3	OTHER CLINICAL / NON-CLINICAL STUDIES	
1.2.3.1	PHASE 1 STUDIES	.16
1.2.4	CLINICAL ADVERSE EVENT PROFILE	.16
1.2.4.1		

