4.3.1 Screening Visit and Observation Phase

Approximately 800 subjects will be screened in this study.

Before any study procedures are performed, subjects must sign informed consent. After informed consent has been signed, subjects will be entered in the IWRS. The subject's migraine history and medical history will be collected at the screening visit. Subjects will also undergo all screening procedures as detailed in Table 1. Subjects will complete daily evening reports electronically (either on a provisioned device, the subject's personal smart phone, or a backup web portal) to report if a migraine occurred, the intensity of the migraine and whether or not the migraine was treated with migraine standard of care medication. Subjects will record medications on a concomitant medication log. The Observation Phase is 28 days, +/- 2 days. After completion of the Observation Phase subjects will return to the study site for the prebaseline visit. In this study, subjects may be screened only once; rescreening is not permitted. The screening visit must be conducted in person.

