4.3.3 Baseline Visit

The baseline visit should occur within 28 days (+/- 2 days) of the screening visit. If the pre-baseline laboratory test results are determined to be unacceptable per protocol, the subject is considered a screen failure and must return to the study site to return the provisioned device (if applicable). Eligible subjects will be dispensed study drug at this visit. This visit must be conducted in person.

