## **7 CONVENTIONS**

### **7.1 Derived Dates**

Derived dates for defining analysis periods are defined as follows:

- Study drug date/time: Complete finding date/time corresponding to “yes” response to question about taking study medication and number of sprays  $> 0$  in the eDiary evening report or medication reconciliation form.
- Study drug start date/time: Earliest study drug date/time.
- Study drug end date/time: Latest study drug date/time.
- Study drug last date/time: Study drug end date/time derived only for subjects with non-missing response to the question “Did the subject complete the study?” on the Study Exit Status CRF. Thus, in an interim analysis, all post-baseline data are included for a subject who is still on study. At the last database lock, the study drug last date is equal to the study drug end date.
- LTT start date/time: Earlier of (1) study drug start date/time, and (2) IWRS baseline visit date (i.e., Baseline/Day 1 visit date from the BHV3500\_202 IWRS Visit Report csv file).
- LTT end date/time: Later of (1) latest complete finding date/time in the eDiary on or after the LTT start date/time, and (2) latest complete visit date on or after the LTT start date through the Week 52/Early Termination visit date, and excluding the Follow-up Week 2 visit date, from the Visit Date CRFs.

- LTT last date/time: LTT end date/time derived only for subjects with non-missing response to the question “Did the subject complete the study?” on the Study Exit Status CRF. Thus, in an interim analysis, all LTT data are included for a subject who is still on study. At the last database lock, the LTT last date is equal to the LTT end date.
- OP start date/time: Earliest complete finding date/time in the eDiary before the LTT start date/time.
- OP end date/time: Latest complete finding date/time in the eDiary before the LTT start date/time.
- COVID-19 visit date: (1) Complete visit date, if it exists; (2) otherwise, complete date the visit was planned to occur for a missed visit (see Section 9.1.1).

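### Pre-treatment diary compliance is divided by a fixed 28 days although the protocol allows 26 or 27 between screening and baseline, so it is understated for short observation phases

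*SAP*

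**What the plan says.** SAP 6.2.6.2 tabulates eDiary usage compliance for the safety analysis set over two periods. For the first, "Last 28 days before LTT start", the numerator is the number of data days from LTT start minus 28 to LTT start minus 1, and the denominator is 28 for every subject. For the second, LTT start to LTT end, the denominator is the subject's own number of days. On the numerator the SAP says: "Data days are records with complete eDiary finding dates". On presentation it says: "eDiary usage compliance is tabulated as a continuous variable and as the number and percentage of subjects in the following categories", and the two categories are at least 90% and at least 80%.

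SAP 7.1 fixes the end of the window: "LTT start date/time: Earlier of (1) study drug start date/time, and (2) IWRS baseline visit date". In the normal course this is the baseline visit date.

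The length of the period comes from the protocol. Section 4.3.1 says: "The Observation Phase is 28 days, +/- 2 days". Section 4.3.3 says: "The baseline visit should occur within 28 days (+/- 2 days) of the screening visit". The synopsis places the start of diary recording after screening: "Upon completion of the screening visit, subjects will electronically" record migraine occurrence each day. It does not say whether the evening of the screening day is the first reporting day.

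**The concern.** A subject whose baseline visit is 26 or 27 days after screening is within the protocol window, yet the 28-day look-back reaches one or two days before screening. No report was possible on those days, and the formula treats them as missed. The error goes in one direction only: compliance is understated or unchanged, never overstated.

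The pre-treatment row is therefore not on the same footing as the LTT row beside it, which uses each subject's own days. This row is the plan's summary of how complete the diary was before treatment, so a reader judging the observation-phase data would naturally turn to it. What is at stake is the accuracy of that description and nothing further.

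**Working it through.** The plan states no compliance result to reproduce, so the check applies its formula to each permitted length.

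**Inputs.** Denominator 28 and cuts of 90% and 80% (SAP 6.2.6.2). Screening-to-baseline interval of 26 to 30 days (Protocol 4.3.1 and 4.3.3). LTT start taken as the baseline visit date (SAP 7.1).

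**Possible diary days.** With screening on day 0 and baseline on day L, the days before LTT start are 0 to L − 1. That gives n = min(L, 28) possible days in the window if the screening evening counts, and n = min(L − 1, 28) if reporting starts the next day.

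**Formulas.** With m missed reports, the SAP figure is 100 × (n − m)/28 and the figure on possible days is 100 × (n − m)/n. The gap is largest at m = 0, where it equals 100 × (1 − n/28): 3.6 points for n = 27, 7.1 for n = 26 and 10.7 for n = 25.

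**Days needed.** 0.9 × 28 = 25.2, so the 90% row needs 26 data days. 0.8 × 28 = 22.4, so the 80% row needs 23.

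**Results for n = 26 and 27** (screening evening counts, L = 26 or 27):

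| Possible days | Missed | SAP figure | On possible days | Row lost |
|---|---|---|---|---|
| 26 | 0 | 92.9% | 100% | none |
| 26 | 1 | 89.3% | 96.2% | 90% |
| 26 | 2 | 85.7% | 92.3% | 90% |
| 26 | 4 | 78.6% | 84.6% | 80% |
| 26 | 5 | 75.0% | 80.8% | 80% |
| 27 | 0 | 96.4% | 100% | none |
| 27 | 1 | 92.9% | 96.3% | none |
| 27 | 2 | 89.3% | 92.6% | 90% |
| 27 | 5 | 78.6% | 81.5% | 80% |

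With 28 or more possible days the two figures agree.

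**Next-day start.** L = 26 leaves n = 25, and full compliance gives 25/28 = 89.3%, so the 90% row cannot be reached. L = 27 and L = 28 leave 26 and 27 possible days, so the table above then applies to them, including subjects exactly on the nominal schedule.

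**Illustration for the whole table.** The documents give neither the spread of visit dates nor the completion rate. The figures below assume independent daily reporting and L spread evenly over 26 to 30 days. They show the share of subjects in the 90% row by the SAP formula, against the share on possible days.

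| Daily completion | Screening evening counts | Next-day start |
|---|---|---|
| 95% | 67.6% v 84.5% | 50.9% v 85.2% |
| 98% | 88.7% v 98.3% | 69.1% v 98.4% |

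The visit spread drives these results. If the screening evening counts and no subject has L below 28, the shift is zero. If every subject had L = 26, at 95% completion the row would read 0.95^26 = 26.4% against 86.1%.

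**The case against.** The strongest defence is that the parameter does what its label says. It measures coverage of a fixed window equal to the nominal phase, and its formula is printed. Compliance is also summarised as a continuous variable, and time in the observation phase is tabulated separately (SAP 6.2.6.1), so short phases are not hidden. This stands in part. However, the row is presented as compliance beside an LTT row with a subject-specific denominator, and the aggregate table of phase length does not let a reader correct the percentages.

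A second defence is that short windows may be rare. Protocol 4.3.1 has subjects return for the pre-baseline visit after the observation phase is complete, and that visit may be up to 5 days before baseline. On that reading a 26-day phase can still leave 28 or more diary days before LTT start. The synopsis instead places the pre-baseline visit within the phase, and 4.3.3 times baseline from screening with the same 2-day tolerance. The documents do not settle the matter, so the frequency is unknown. This objection stands against any claimed percentage shift, but not against the formula being wrong for a subject whose interval is 26 or 27 days.

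Two stronger readings are tempting. A reader might infer that fully compliant subjects with short phases generally drop below 90%. They do not: with 26 or 27 possible days they score 92.9% or 96.4%. The inference holds only for baseline on day 26 combined with a next-day start, which the documents do not state. Table 1 as extracted marks the migraine report under the Observation Phase and not under the Screening Visit, which hints at a next-day start. Evening reporting once the screening visit is complete, with the device set up at that visit, points the other way.

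A reader might also infer that the migraine-day baseline is distorted. It is not: SAP 6.4.6.1 prorates observation-phase migraine days by actual data days, and the migraine analysis set requires 14 days of data, not a compliance percentage. The deviation for compliance below 80% uses LTT start to end only (SAP 9.2), and exclusion criterion 6g rests on the investigator's opinion, with no threshold.

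**Conclusion.** The point holds in a limited form. The fixed denominator counts impossible days as missed for subjects with 26 or 27 days between screening and baseline. If the screening evening counts, the understatement is at most 7.1 points, and subjects with one or two missed reports of 26, or two of 27, are wrongly placed below 90%. The 80% row is wrong for four or five missed of 26 and for five of 27. If reporting starts the next day, the maximum understatement is 10.7 points and the problem extends to subjects with a 28-day interval.

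These per-subject figures rest only on the SAP formula, the protocol window, LTT start falling on the baseline visit date, and the stated choice of first reporting day. The population figures rest on an assumed visit spread and completion rate and are illustrative. The consequence is confined to one descriptive table, so this is a minor correction, worth making because the reported percentage is wrong and easily put right.

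**What to change.** In SAP 6.2.6.2, replace the pre-LTT denominator of 28 with the smaller of 28 and the number of days from the first day on which an evening report was possible to LTT start minus 1. State whether that first day is the screening visit date or the day after, so that no impossible day remains in the denominator, and count numerator days over the same interval.

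The SAP's OP start date should not serve as the first day. SAP 7.1 derives it as "Earliest complete finding date/time in the eDiary before the LTT start date/time", so reports missed at the beginning of the phase would drop out of the denominator and compliance would be overstated. The screening visit date avoids this.

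The cost is about one line of SAP text and one line of programming. Results for subjects with 28 or more possible days do not change, and no new data are needed.
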